### Clinical Investigation Plan

Automatic Control of Total Intravenous Anesthesia: Closed-loop Delivery of Propofol and Remifentanil Using Bispectral Index as Feedback Variable.

Acronym: ACTIVA 2. Id code: NP-2861. NCT number: NCT04432974.

- Postoperative sedation. It is assessed by means of a Sedation Score scale. It is a 3 point scale from 0 (fully awake) to 3 (fully sedated).
- Postoperative nausea and vomiting (PONV). It is assessed by means of the Bellville PONV scale. It is a 3 point scale from 0 (no nausea and vomiting) to 3 (vomiting present).
- Postoperative analgesia. It is assessed using a 10-point numeric rating scale (NRS). It is a 10 point scale from 0 (no pain) to 10 (maximum pain).

## Measured variables

For each patient enrolled in the study, the following variables will be collected:

- Age.
- Gender.
- Weight
- Height
- Type of surgical procedure
- Anesthesiological risk assessment according to the American Society of Anesthesiologists (ASA) physical status classification system.
- PONV risk assessment according to the Apfel simplified risk score.

These data are collected by the principal investigator at patient arrival in the operating room, before surgery and they are noted on the patient's anesthesiology clinical record form.

The following variables are automatically collected by the ACTIVA software, they are recorded in real-time every second and stored on a ".csv" file:

- HR.
- Peripheral oxygen saturation.
- MBP.
- BIS.
- BIS signal quality index (SQI).
- Burst suppression ratio.
- Infusion rates of propofol and remifentanil.

The following data are collected by the principal investigator after surgery and noted on the patient's anesthesiology clinical record form.

- System dysfunctions.
- Level of satisfaction of the experimenter.
- HR.
- MBP.
- Postoperative sedation.

---

 Burst suppression is defined as a period on the EEG trace characterized by attenuated or suppressed signal (<10 mV) alternating with brief periods of cortical activity, precisely termed 'bursts.' More than 50% of this period is dominated by attenuated/suppressed activity. This effect may sometimes be intentionally induced, for example, during neuroanesthesia, as a protective measure against cerebral ischemia, as it coincides with a reduction in cerebral metabolism. However, it is important to consider that it is also associated with a higher incidence of postoperative delirium.

## Clinical Investigation Plan

Automatic Control of Total Intravenous Anesthesia: Closed-loop Delivery of Propofol and Remifentanil Using Bispectral Index as Feedback Variable.

Acronym: ACTIVA 2. Id code: NP-2861. NCT number: NCT04432974.

- PONV.
- Postoperative analgesia.

## Participation criteria

The population considered in the clinical study consists of adult patients scheduled for elective surgery for whom total intravenous general anesthesia is indicated, using the hypnotic drug propofol and the analgesic drug remifentanil, and who have provided appropriate informed consent. Patients under the age of 18 and patients incapable of understanding and consenting are excluded from the study.

The selection of patients is made regardless of age (provided they are over 18), gender, weight, height, as well as anesthetic risk and the type of surgical procedure. This reduces systematic errors associated with specific patient selection for enrollment in the study.

## Enrollment procedure

The enrolled patients underwent an anesthesiological treatment conducted in a closed-loop system following the clinical protocol and under the constant supervision of the experimenter. The experimentation took place in a single operating room at the experimenter's center where plastic surgery procedures are performed. This allowed for maintaining a consistent surgical and environmental setting.

Patients are informed of the possibility to participate in the study during the preoperative anesthesia visit, which typically occurs two weeks before the surgical procedure. If the patient chooses to participate in the study, informed consent is obtained before the start of the medical procedure subject to the experimentation.

The patient enrolled in the study arrives in the operating room on the day of the procedure and undergoes the standard preoperative preparation, which is administered to all patients undergoing intravenous general anesthesia, regardless of their enrollment in the study. In particular:

- Venous access is established.
- Instrumental monitoring includes blood pressure, electrocardiogram, peripheral oxygen saturation, and BIS (Bispectral Index).
- Infusion pumps are connected to the venous access.

The ACTIVA control software is then initiated by the lead experimenter, who enters the necessary anthropometric data into the GUI, initializes the system, and starts the automatic control. During the surgical phase, the experimenter supervises the system and ensures its proper functioning. If necessary, annotations are added to the system according to the protocol. Once the surgical procedure is completed, the experimenter stops the drug infusions through the GUI but continues recording the BIS and other patient monitoring parameters. The patient awakens spontaneously. After awakening, the ACTIVA software is turned off by the experimenter.

The patient is then transferred to the recovery room where they undergo standard post-operative procedures. The study concludes 24 hours after the patient awakens from anesthesia with a postoperative anesthesia visit.

## Clinical Investigation Plan

Automatic Control of Total Intravenous Anesthesia: Closed-loop Delivery of Propofol and Remifentanil Using Bispectral Index as Feedback Variable.

Acronym: ACTIVA 2. Id code: NP-2861. NCT number: NCT04432974.

## Number of patients enrolled

The sample size was determined based on the primary outcome measure concerning the depth of hypnosis adequacy provided by the ACTIVA control software. Specifically, it was calculated with the aim to assess the proportion of patients for whom the percentage of the anesthesia maintenance duration in which the BIS is kept inside the recommended range from 40 to 60 is greater than 43%. This latter value is the average percentage that was observed in a previous data acquisition campaign concerning manually controlled TIVA, which was performed in the same clinical setting considered for the present clinical trial (Study acronym: ACTIVA 1, Id code: NP-1843).

The proportion was estimated to be 90% of patients with a 95% confidence interval and a margin of error of 10%. The resulting sample size is 139 patients. This number of enrolled subjects also ensures that the ACTIVA control software is adequately tested for safety, reliability, feasibility, and applicability. Secondary outcome measures were not considered in the sample size calculation.

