### Clinical study description

The clinical study ACTIVA 2 is a pragmatic, interventional, nonrandomized, single-arm, single-center.

The investigation is for research purposes (for publication in scientific journals), non-commercial, and for clinical development of the ACTIVA control software.

The primary outcome measure is the depth of hypnosis adequacy. It is assessed by means of the percentage of the anesthesia maintenance duration in which the BIS is kept inside the recommended range from 40 to 60. The percentage of the anesthesia maintenance duration in which the BIS is kept below 40 is also specified. Maintenance duration is the period of time that goes from the end of anesthesia induction to the point at which the automatic control is turned off at the conclusion of surgery. The end of anesthesia induction is defined as the time instant when the BIS drops below 40 for the first time and remains there for the subsequent 30 seconds.

The secondary outcomes measures are:

- Number and types of dysfunctions of the ACTIVA automatic infusion system.
- Level of satisfaction of the experimenter. It is expressed on a scale from 0 to 10 regarding the ease of use of the ACTIVA software and its infusion system, the induction phase of anesthesia and the maintenance phase of anesthesia.
- Effect of drugs delivery on heart rate. It is assessed by means of the percentage of the anesthesia maintenance duration in which the heart rate (HR) is kept inside the range from 50 to 100 beats per minute. The percentage of the anesthesia maintenance duration in which the HR is kept below 50 is also specified.
- Effect of drugs delivery on mean blood pressure. It is assessed by means of the percentage of the anesthesia maintenance duration in which the non-invasively measured mean blood pressure (MBP) is kept inside the range from 65 to 110 mmHg. The percentage of the anesthesia maintenance duration in which the MBP is kept below 65 is also specified.
- Postoperative heart rate stability. It is assessed by measuring the HR in bpm.
- Postoperative Mean Blood Pressure Stability. It is assessed by non-invasive measuring of the mean blood pressure in mmHg.

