## Subject Enrollment Count

All subjects enrolled in the clinical investigation (including patients withdrawn from the study before its initiation who have provided informed consent and patients lost to follow-up) must be counted and documented. If a subject withdraws from the study, the reasons should be documented and recorded. These patients will not be included in the sample size calculation for the study or in the primary or secondary objectives.

Patients who are withdrawn from the study before the initiation of the ACTIVA software due to device safety, reliability, or feasibility issues are considered enrolled in the study and will be followed throughout the study's duration.

Patients who discontinue the study during the operation of the ACTIVA software are considered fully enrolled, and all available data will be analyzed.

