## Statistical analysis

The statistical analysis consists in the descriptive statistics of the collected data.

Synthetic statistical data are calculated for all study variables.

For quantitative data mean and standard deviation, or median and interquartile range are calculated according to data distribution. Data normality is checked by using the Shapiro-Wilk test.

Categorical variables are synthesized by using patient count and percentage of patients belonging to each category.

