### Selection bias at the time of analysis.

The clinical trial requires that closed-loop anesthesia be practiced from the initiation of the ACTIVA software until the end of the surgical procedure. However, it may happen that:

- The primary experimenter decides to interrupt the software; in this case, it must be recorded in the report file.
- The software or its components (monitors, infusion pumps) may cease to function correctly; in this case, the system is halted and switches to manual mode or requires the experimenter's intervention. The experimenter must record the event in the report file. If the above occurs, it is the responsibility of the experimenter to assess the possibility of including in the data analysis what has been collected up to the moment of system interruption.

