¹ Burst suppression is defined as a period on the electroencephalogram trace characterized by attenuated or suppressed signal (<10 mV) alternating with brief periods of cortical activity, precisely termed 'bursts.' More than 50% of this period is dominated by attenuated/suppressed activity. This effect may sometimes be intentionally induced, for example, during neuroanesthesia, as a protective measure against cerebral ischemia, as it coincides with a reduction in cerebral metabolism. However, it is important to consider that it is also associated with a higher incidence of postoperative delirium.

Statistical Analysis Plan

Automatic Control of Total Intravenous Anesthesia: Closed-loop Delivery of Propofol and Remifentanil Using Bispectral Index as Feedback Variable.

Acronym: ACTIVA 2. Id code: NP-2861. NCT number: NCT04432974.

The following data are collected by the principal investigator after surgery and noted on the patient's anesthesiology clinical record form.

- System dysfunctions.
- Level of satisfaction of the experimenter.
- HR.
- MBP.
- Postoperative sedation.
- PONV.
- Postoperative analgesia.

Descriptive statistics will be performed on all study variables.

Quantitative data will be presented as mean (SD) or median (IQR) according to their distribution. Normality of the data will be tested using a Shapiro-Wilk test. Categorical data will be presented as frequency (proportion).

Data management

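### The 139 patients are justified by the 95% CI for the proportion above 43% time in BIS 40–60, but neither the outcome nor the analysis sections commit to reporting that proportion or any CI, and the rule on interrupted cases is unsettled

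*Protocol*

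**What the plan says.** **Sizing.** Protocol, Number of patients enrolled, and SAP, Sample size calculation, use the same text. Of the sample size they say that "it was calculated with the aim to assess the proportion of patients for whom the percentage of the anesthesia maintenance duration" spent at BIS 40 to 60 exceeds 43%. The 43% cut-off is the average time in range under manual control in the earlier ACTIVA 1 data collection. On the assumptions: "The proportion was estimated to be 90% of patients with a 95% confidence interval and a margin of error of 10" per cent, giving 139 patients.

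**Outcomes.** Protocol, Clinical study description, and SAP, Outcomes, define the primary outcome for each patient as the "percentage of the anesthesia maintenance duration in which the BIS is kept inside the recommended range from 40 to 60", with the percentage below 40 also given. No 43% cut-off and no proportion of patients above it appears there, among the secondary outcomes, or among the collected variables.

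**Analysis.** The SAP states "Quantitative data will be presented as mean (SD) or median (IQR) according to their distribution", and frequencies with proportions for categorical data. The protocol's Statistical analysis section does the same: "Categorical variables are synthesized by using patient count and percentage of patients belonging to each category". A confidence interval is mentioned only in the two sample-size sections.

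**Interrupted cases.**
- Protocol, Subject Enrollment Count: "Patients who discontinue the study during the operation of the ACTIVA software are considered fully enrolled, and all available data will be analyzed".
- Protocol, Deviations from the clinical evaluation plan: patients who do not complete because of software problems or by investigator decision are still evaluated for the primary outcome.
- Protocol, Selection bias at the time of analysis: when the system is interrupted, "it is the responsibility of the experimenter to assess the possibility of including in the data analysis what has been collected" up to that moment.

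**The concern.** A study sized by the width of an interval should report that interval. Here the estimate appears as an aim in the sample-size text and is then dropped from the sections that say what will be reported. A report could follow the plan in full and never show how many patients exceeded 43%, or how precisely that is known.

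The second issue is separate and affects any summary of the primary outcome, including the mean or median. Protocol, Instrument-phenomenon interaction, allows a switch to manual mode when BIS cannot be held in range although the software seems to work. Some interrupted cases may therefore be those with poor control. If the experimenter decides afterwards whether their data count, the result can depend on that decision.

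**Working it through.** **1. Reproducing 139.** Inputs from the sample-size sections: p = 0.90, 95% confidence (z = 1.96, two-sided assumed), 10% margin. Formula: n = z² × p × (1 − p) / d², where d is the half-width.
- d = 0.05 (10% as total width): 1.96² × 0.9 × 0.1 / 0.05² = 138.3, so 139. This matches.
- d = 0.10 (10% as half-width): 1.96² × 0.9 × 0.1 / 0.10² = 34.6, so 35. This does not match.

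So 139 comes from interval precision for this proportion, at ±5 points. The ±5 is inferred from the arithmetic; the documents say only 10%.

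**2. Do the planned summaries deliver it?** A mean with SD does not give the share of patients above 43%. A median with IQR gives at best a bound: a lower quartile above 43% shows that at least about 75% of patients exceed it, but cannot show whether the share is near 90%. The line on categorical data would give a count and percentage only if the dichotomy were declared a variable, and would still give no interval.

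**3. What the missing result would look like.** 0.9 × 139 = 125.1, so take 125/139 = 89.9%.

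| Method | 95% CI | Width (points) |
|---|---|---|
| Wilson | 83.8% to 93.9% | 10.1 |
| Clopper-Pearson | 83.7% to 94.4% | 10.7 |

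**4. Effect of discretion over interrupted cases.** Assumption: 139 started, 125 above 43% and 14 not, and 7 interrupted cases (5%) are left out. The documents give no such number. If j of the 7 are not above 43%, the estimate is (125 − (7 − j)) / 132 = (118 + j) / 132.

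| j | Estimate | Change from 89.9% (points) |
|---|---|---|
| 0 | 118/132 = 89.4% | −0.5 |
| 1 | 119/132 = 90.2% | +0.2 |
| 7 | 125/132 = 94.7% | +4.8 |

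The last row needs half of all 14 patients not above 43% to be among those omitted. It is a limit, not a forecast.

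**The case against.** The strongest defence is that the plan is not silent. The sample-size text, repeated in the SAP, names the proportion and ties it to the primary outcome. The proportion can be derived from the listed outcome and the stored BIS data, and the line on categorical data could cover it. The study is single-arm and descriptive, with no test or success criterion, so no decision in the documents hangs on the interval. A reader given x/n could compute it.

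Most of this stands, and it limits the weight of the point. It does not remove it: stating an aim when justifying N is not a commitment to report, nothing requires x/n to be published, and an interval is fully compatible with a descriptive plan.

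On interrupted cases, the discretion may concern only whether partial data are usable, not whether the patient is removed. Interruptions may also follow pump or monitor faults that say nothing about BIS control. Both are fair, and they are why no direction can be claimed. The sections still need reconciling, because the SAP's Population to be analyzed section restates eligibility and procedures without settling the matter.

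Three stronger readings are tempting, and the documents support none of them:
- That 139 is wrong because a 10% margin gives 35. The figure follows from the stated inputs once 10% is read as total width; only the wording is unclear.
- That the proportion is the true primary outcome and has been replaced. Both outcome sections consistently name the continuous percentage.
- That the result will be inflated by nearly 5 points. That requires every omitted case to be not above 43%, and the documents give neither the number nor the BIS results of interrupted cases.

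**Conclusion.** The point holds and should be fixed. The estimate and precision that justify 139 patients are stated only as a sizing aim; the outcome and analysis sections do not secure them. The cost is an unreported result of roughly ±5 points around 90%, not a wrong sample size or an invalid primary outcome.

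The conflict over interrupted cases is a distinct weakness that could bias any primary-outcome summary. Under the assumption of 7 omitted from 139, the proportion lies between 89.4% and 94.7%. The upper end is a shift about as large as the inferred 5-point half-width, but neither size nor direction can be determined from the documents.

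**What to change.** Keep the continuous percentage as primary outcome and N = 139. Add to SAP Outcomes and Analyses:

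> The proportion of patients with BIS 40–60 for more than 43% of maintenance will be reported as x/n with a two-sided 95% CI (Wilson or Clopper-Pearson, named in advance). The denominator is all patients in whom ACTIVA automatic control was started, including those who discontinued or were switched to manual control. For patients switched early, maintenance ends for this analysis when automatic control stops. Patients with no evaluable maintenance period count as not above 43%; their number is stated, and a sensitivity analysis excludes them.

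Replace the experimenter's discretion in Protocol, Selection bias at the time of analysis, with this rule. It agrees with Deviations from the clinical evaluation plan and with the last paragraph of Subject Enrollment Count. Subjects withdrawn before ACTIVA was started stay outside this denominator and are counted separately.

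In both sample-size sections, state the precision as about ±5 points (total width about 10). Either interval is slightly wider than 10 points at 125/139. Holding ±5 points exactly at 90% would need 141 patients (Wilson) or 158 (Clopper-Pearson), so the word 'about' is needed if N stays at 139.

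Cost: a few lines of text and a short calculation on per-second BIS data already stored. No new data are needed. The estimate may turn out less favourable.

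### A 10% margin of error gives 35 patients, not 139; 139 is the size for a margin of 5 percentage points

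*Protocol*

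**What the plan says.** The Protocol section Number of patients enrolled bases the size on the primary outcome, recast as a responder proportion: the share of patients for whom the percentage of maintenance time in which "BIS is kept inside the recommended range from 40 to 60 is greater than 43" per cent. It then gives the planning values, "The proportion was estimated to be 90% of patients with a 95% confidence interval and a margin of error of 10" per cent, and the outcome of the calculation, "The resulting sample size is 139 patients". The SAP section Sample size calculation repeats this wording.

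Neither document gives the formula. Neither says whether the 10% is a half-width or a full width, or whether it is absolute or relative. No dropout allowance is stated. On withdrawn patients, the Protocol section Subject Enrollment Count says "These patients will not be included in the sample size calculation for the study or in the primary or secondary objectives". There is no null value, power or hypothesis test; under Statistical analysis the Protocol states: "The statistical analysis consists in the descriptive statistics of the collected data".

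**The concern.** The margin of error of an estimate is ordinarily the half-width of its confidence interval. Read that way, the stated inputs lead to about a quarter of the stated sample size.

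This paragraph is the only quantitative justification of the trial size, and other parts of the Protocol lean on it. Risks/benefits ratio refers to the sample size calculation, and Declaration of Compliance asserts that the number of observations is sufficient. A reader who takes the text at face value can go wrong in two ways:

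- They may conclude that 139 − 35 = 104 more patients are exposed than the declared precision needs, in what the Protocol describes as the first clinical investigation of this system.
- They may expect an interval of about 80% to 100% around a 90% estimate, when the design delivers about 85% to 95%.

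Because the SAP repeats the statement, it does not correct the Protocol, and a publication could carry the error forward.

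**Working it through.** **Inputs** (Protocol, Number of patients enrolled; the same in the SAP, Sample size calculation)

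- Anticipated proportion p = 0.90, so p(1 − p) = 0.09.
- Confidence level 95%, taken as two-sided because sidedness is not stated: z = 1.95996, z² = 3.84146.
- Margin d = 10% as stated.
- Stated result n = 139.
- The 43% threshold defines a responder and does not enter the formula.

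**Formula.** Normal approximation for one proportion: n = z² p(1 − p) / d², with numerator 3.84146 × 0.09 = 0.34573.

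**Trying to reproduce 139**

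| Reading of the 10% | d | n before rounding | n |
|---|---|---|---|
| Half-width of 10 points, as worded | 0.10 | 0.34573 / 0.0100 = 34.57 | 35 |
| Relative margin, 10% of 90% | 0.09 | 0.34573 / 0.0081 = 42.68 | 43 |
| Total width of 10 points | 0.05 | 0.34573 / 0.0025 = 138.29 | 139 |

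Only the last row returns the plan's figure, and it does so exactly.

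**Other ways to reach 139 with a 10-point margin**

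| Variant | n |
|---|---|
| Worst-case p = 0.5 | 97 |
| 99% confidence | 60 |
| One-sided 95% | 25 |
| Continuity correction | 45 |
| Wilson interval, half-width at most 10 points | 37 |
| Wilson interval, lower arm at most 10 points | 62 |
| Clopper-Pearson interval, half-width at most 10 points | 44 |
| Clopper-Pearson interval, lower arm at most 10 points | 65 |

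None gives 139. Inflating 35 to 139 for dropout would need a loss of 1 − 35/139 = 74.8%, and no loss is assumed. A two-sided one-sample test of 80% against 90% with 90% power needs 137. That is close, but it is not 139, and the documents state no null value, power or test.

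**Precision delivered**

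- n = 139, p = 0.90: half-width 1.95996 × √(0.09/139) = 0.0499, or 4.99 points (total width 9.97 points).
- n = 35, p = 0.90: half-width 1.95996 × √(0.09/35) = 0.0994, or 9.94 points.
- If 125 of 139 patients respond (89.9%), the 95% interval is 84.9% to 94.9% (Wald), 83.8% to 93.9% (Wilson) or 83.7% to 94.4% (exact).

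**The case against.** The strongest reply is that this is a labelling error and not a sizing error. If 10% was meant as the total width of the interval, 139 reproduces exactly. The mistake is also conservative, and nothing in the planned analysis uses the margin: both documents plan descriptive statistics only, with no confidence interval, test or success criterion. The Protocol adds that 139 patients also serve to test safety and feasibility, so precision is not the only reason offered for the number. Finally, since no formula is given, a reviewer cannot be certain that 5 points was intended.

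Much of this stands. The sample size is not wrong, no estimate is biased, and the conduct of the trial is unaffected. The total-width reading, however, confirms that the wording is wrong: the text says margin of error, and nothing in either document lets a reader recover the other meaning. The safety and feasibility remark carries no number, and the text presents 139 as the result of the proportion calculation. The doubt about intent is small, because the 5-point reading is the only one tried that returns 139, but the sponsor should confirm it when making the edit.

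**Conclusion.** The concern holds. As written, the inputs give 35 patients and the plan states 139: a factor of about four in sample size (139/35 = 3.97) and about two in precision (9.94 against 4.99 points). The figure of 139 belongs to a margin of 5 percentage points, that is, a total 95% interval width of 10 points.

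This rests on a two-sided 95% interval, the normal approximation, an anticipated proportion of 90% and the ordinary meaning of margin of error. Treating the 10% as relative does not rescue the statement, since it gives 43. The fault lies in the stated precision, in both documents. The trial is not undersized for this aim.

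**What to change.** In the Protocol (Number of patients enrolled) and the SAP (Sample size calculation), replace the 10% margin of error with: *a margin of error of 5 percentage points (total 95% confidence interval width 10 points, normal approximation)*. Keep 139 patients. The sponsor should confirm that this was the calculation performed.

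Add that with 125 responders among 139 patients the exact 95% interval would be about 84% to 94%. Label it as exact, because at 83.7% to 94.4% it is 10.7 points wide, slightly more than the normal-approximation width.

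The cost is a short edit in each document, with no extra patients and no change to trial conduct.
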